Sub Aim II- Determine the kinematic dissociation between trunk and pelvis during the gait cycle. Determine the change in trunk to pelvis angle (uprightness).

Hypothesis: In the SMA walking and after-assist condition, the peak angle of dissociation between trunk and pelvis will demonstrate evidence of increased stability relative to the control condition.

Specific Aim III: Determine the effectiveness of the HWA to alter **STAIR** ascend/descend test (Flansbjer, Holmbäck, Downham, Patten, & Lexell, 2005) scores in individuals post-stroke. Determine the changes in paretic and non-paretic limb EMG magnitudes at critical stair climbing timepoints.

Hypothesis: In the HWA walking condition, stair ascent and descent times will be reduced compared to the control condition.

Specific Aim IV: Determine the effect of the HWA on the magnitude of **ground reaction forces** (vertical load, horizontal shear, vector patterns, and center of pressure) for both lower extremities in individuals post-stroke.

Specific Aim V: Determine the effect of the HWA on **Spatial and Temporal gait variables** (Gait speed, step length, stride length, stride symmetry, step width, cadence) in individuals post-stroke.

Exploratory Aim VI: (Exploratory ONLY- not a study outcome) Appling inverse dynamic mathematics, we will develop our methods for internal joint moment measurement and analysis using hip joint data.

Participant Eligibility:

Potential participants will be recruited through networking with local care providers (letter attached) fliers (flier attached) and word of mouth. Those who express interest in study participation will be screened over the phone or in person to determine if they meet study criteria (below) before beginning the process of obtaining written informed consent (consent form is also attached).

Inclusion criteria

- 1. ≥12 weeks but <1 year post stroke at time of study participation
- 2. Age: 18-85 years
- 3. Ability to walk a minimum of 10 meters with standby assistance with or without orthosis or assistive device (Functional Ambulation categories 3, 4 or 5)
- 4. Able to follow three step commands
- 5. Express the ability to understand study tasks and purpose
- 6. Able and willing to provide written informed consent
- 7. Living in the community with the ability to travel to maurices Community Clinic for testing
- 8. Willingness to wear the StepWatch pedometer for a period of 3 days in their home

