- measure of sensitivity thought to reflect A α axon transmission. (Rolke et al., 2006) It will be quantified in seconds and scored using the average of three trials with a 128 Hz tuning fork placed on the skin at the base of the great toenail. (Janz, Bjorkland, Kramer, Oczak, & Borstad, 2018)
- 6. The StepWatch Activity Monitor will be used to characterize participants physical activity based on their daily step counts. Participants will wear StepWatch Activity Monitor on the less affected lower extremity during their daily routines for 8 hours per day for three days. Verbal and written instructions will be provided. The StepWatch is reliable and has been validated to provide the most accurate measurements of physical activity in persons with slow walking, such as may be caused by stroke. (Mudge, Stott, & Walt, 2007) (Mudge & Stott, 2008) Physical activity as measured by daily step count is a potentially large source of variability within the participants that will be important to characterize and understand. In Specific Aims 1 and 2 we will be attempting to quantify a differenced between the control condition and the aftereffect of walking with the HWA. Because we hypothesize that aftereffect will be greater in individuals with less lower extremity use (those who take fewer steps) since their stroke it is important to collect data on this variable.

Description of measures used to quantify effect of HWA on walking

- 7. Kinematic Analysis of Gait will be obtained using a Qualisys 8-camera motion capture system. Sample rate 120 Hz. A modified IOR gait marker set (~40 markers) applied bilaterally. (Cappozzo, Catani, Della Croce, & Leardini, 1995)
- 8. Analysis of muscle activation during gait using 16 Delsys Tringo EMG sensors applied over bilateral LE muscle groups including gluteus maximus (1), quadriceps (3), hamstrings (2), tibialis anterior (1), medial gastrocnemius (1), totaling 8 sensors per lower extremity. Sample rate 2000Hz
- 2 AMTI Force platforms will be used to quantify ground reaction forces (vertical load, horizontal shear, vector patterns, and center of pressure) for both lower limbs during gait. Sample rate 1200Hz.
- 10. Stair Climbing Ascent/Descent test- A timed test of the ability to ascend and descend stairs with our without a rail. For this study a flight of 7 stairs will be used. The means of two trials of ascending and descending will be recorded. (Flansbier et al., 2005)

Withdrawal or removal of participants from the study

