In the case that a participant, for any reason, does not complete the study the following categories will be used to record the occurrence:

- 1. Patient withdraws
- 2. Patient is unable to perform protocol requirements
- 3. Patient demonstrates a change in medical condition
- 4. Patient experiences an adverse event that makes continuation in the protocol unsafe
- 5. PI determines that continuation in the study would not be appropriate
- 6. Other

Study Risks:

This is a study of walking performance therefore risk of falling is present. This risk is similar
to the risk one would undertake while participating in outpatient physical therapy for walking
training following stroke. It will be mitigate by study personnel maintain contact with the
participant during walking, transitions and stair climbing. Participants will be encouraged to

- wear their most comfortable walking shoes and will be walking in a well-lit, open environment.
- 2. While the adhesive materials used in this study are latex free, the risk of skin irritation is present. Skin irritation could arise from the tape used to fix the motion capture markers, the EMG sensors or from the HWA device itself rubbing on the skin. This risk will be discussed with the participants during the process of obtaining informed consent and they will be instructed to inform study personnel if they experience itching or irritation. Participants who demonstrate somatosensory impairment may not feel skin irritation. Those participants will receive a visual skin check in areas of possible irritation midway through the assessments. Adjustments to the size and fitting of the HWA will be conducted to address skin irritation including the possibility of adding additional padding or other measures to reduce irritation.
- The HWA device delivers a maximum 4 Nm of torque to the legs during walking. There is a
 chance that the device could malfunction during use, which could cause a loss of stability or
 balance. To mitigate this risk study personnel will maintain contact with study participants
 during device use.
- 4. There is a possible risk that study participants may develop muscle soreness from the walking or stair climbing they will perform in as part of the assessments. To mitigate this risk participants will be given scheduled rest periods during the protocol and allowed to take additional rest if they choose.

Statistical considerations and Data Management

Study design

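### Aim III compares stair times, but no rule covers a participant who cannot complete the flight, so the comparison as written uses only people who finish in both conditions

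*Combined protocol and SAP*

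**What the plan says.** - **Hypothesis** (Study Objectives, Specific Aim III): "In the HWA walking condition, stair ascent and descent times will be reduced compared to the control condition". The same aim also covers limb EMG at key points of stair climbing.
- **Measure** (Description of measures used to quantify effect of HWA on walking, item 10): "A timed test of the ability to ascend and descend stairs with our without a rail". The protocol adds: "For this study a flight of 7 stairs will be used. The means of two trials of ascending and descending will be recorded".
- **Conditions** (Testing Plan, Data Set 2): one stair test without the device and one with it, in the same session, with the order differing between Groups A and B. The walking kinematics are collected in a separate session (Data Set 3).
- **Mobility at entry** (Participant Eligibility, inclusion criterion 3): "Ability to walk a minimum of 10 meters with standby assistance with or without orthosis or assistive device", which the criterion equates with Functional Ambulation categories 3 to 5. No inclusion or exclusion criterion mentions stairs.
- **Inability** (Withdrawal or removal of participants from the study, category 2): "Patient is unable to perform protocol requirements". This is one of six reasons for recording that someone did not complete the study.
- **Analysis** (Data analysis plan): paired t-tests and ANOVA at the 0.05 level. No score, time cap, rank or missing-data rule is given for any outcome.

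**The concern.** A completion time exists only if the flight is completed. Whether a participant has a value therefore depends on the ability that the test is meant to measure. A participant who cannot climb without the device but can with it shows a clear benefit, and one who can climb without it but not with it shows a clear harm. Neither has a paired difference in seconds, so neither enters a paired comparison of times. The stair-time result would then describe only people able to climb in both conditions, and could miss an effect in either direction.

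Two smaller gaps follow from the same wording. A participant who completes one trial has a time but no two-trial mean. Withdrawal category 2, read literally, could also class someone who cannot do the stairs as not completing the study, although the walking session is separate.

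**Working it through.** **1. The plan's own figure.** The only sample-size calculation is for peak knee flexion (Sample Size): difference 5°, SD 5°, two-sided 5%, 80% power. The standardised difference is 5/5 = 1.0, and a paired t-test with n = 10 has power 80.3%, so the stated 10 reproduces. No effect, SD or sample size is given for stair times, so Aim III has no figure to reproduce.

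**2. What each pattern contributes.** With t the mean time in a condition:

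| Without HWA | With HWA | Difference in times | Difference in speed, 7/t, with 0 if unable |
|---|---|---|---|
| able | able | t(HWA) − t(control) | 7/t(HWA) − 7/t(control) |
| unable | able | none: pair lost | 7/t(HWA) − 0, positive |
| able | unable | none: pair lost | 0 − 7/t(control), negative |
| unable | unable | none: pair lost | 0 − 0 = 0 |

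Rows 2 and 3 are the discordant pairs. They are lost on the time scale and kept on the scored scale. Row 4 gives a zero difference, which the standard signed-rank test discards, so those people add no information to the test under either approach.

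**3. How likely the gap is to matter.** The documents give no rate of stair inability. Let p be the assumed proportion unable to finish in at least one condition, with 12 participants tested. The chance of at least one is 1 − (1 − p)^12, and the expected number of complete pairs is 12(1 − p).

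| p (assumed) | Chance of at least one in 12 | Expected complete pairs |
|---|---|---|
| 5% | 1 − 0.95^12 = 46% | 11.4 |
| 10% | 1 − 0.90^12 = 72% | 10.8 |
| 20% | 1 − 0.80^12 = 93% | 9.6 |

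Each lost pair is 1/12 = 8% of the sample.

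**4. Does scoring the unable gain power?** This was simulated with values that are all assumed: 12 participants, control stair speed mean 0.50 and SD 0.20 stairs/s, device gain mean 0.07 and SD 0.08, and 2 of 12 expected below the ability threshold without the device. On average 2.1 of 12 pairs are lost. About 0.8 of these are able only with the device and about 1.2 are unable in both conditions.

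| Analysis | Power |
|---|---|
| t-test on times, completers | 0.61 |
| t-test on speed, completers | 0.72 |
| Wilcoxon on speed, completers | 0.68 |
| Wilcoxon on speed, 0 if unable | 0.70 |

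The step from 0.61 to 0.70 is mostly the change to the speed scale, on which the simulated data were built as normal. With the scale and test held fixed, scoring the unable moves power from 0.68 to 0.70. The same like-for-like comparison shows no gain at 1 of 12 and about 0.06 at 3 of 12.

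**The case against.** The strongest reply is that few participants may fail. They live in the community, can travel to the clinic and are in Functional Ambulation categories 3 to 5. The flight is short, a rail is allowed, staff stay in contact and rests are scheduled. This stands as a reason to expect a small number. It does not supply a rule, since none of these features requires stair ability. For another outcome the protocol does acknowledge a capability limit: the dorsiflexion sub aim carries a note that it depends on how many participants can walk safely without an ankle-foot orthosis.

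A second reply is that the data collection forms, attached to the protocol but not available here, may say how a failed attempt is recorded. That is possible, but a form instruction would not by itself settle the analysis.

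A third is that Aim III is not the powered hypothesis. That is correct and limits the weight of the point.

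Some stronger readings are tempting and are not supported:

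- **That the plan explicitly excludes non-completers.** It does not say so. The exclusion follows from comparing times in pairs with no rule for a missing time.
- **That the device will enable some people to climb.** Nothing in the documents shows this. The maximum torque is 4 Nm, which wearers describe as mild to moderate. Discordant pairs could also go the other way, so the direction of any bias is unknown.
- **That scoring the unable recovers power.** The like-for-like figures show little or no gain except at the highest assumed rate.
- **That the 20% dropout allowance or the 0.4 m/s walking speed indicates a stair-inability rate.** The first concerns leaving the study, and the second was used to estimate session time.
- **That all of Aim III is lost for these participants.** Stair EMG from a partial attempt may still be usable.

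**Conclusion.** The point holds for the stair-time comparison. A timed outcome, entry criteria silent on stairs, and a paired analysis with no rule for non-completion together restrict the result to people who finish in both conditions. Discordant pairs are left out whichever way they point. The number affected is unknown. At assumed rates of 5% to 20%, the chance that at least one of 12 participants is affected runs from 46% to 93%, so a rule is likely to be needed unless inability is rare. These figures assume that all 12 are tested and that participants are independent. The stated sample size and the walking aims do not depend on the stair times, provided that a stair non-completer is not recorded as a study withdrawal. The plan should be changed, but the main hypothesis is not threatened.

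**What to change.** Before data are seen, add one paragraph to the Data analysis plan and one code to the stair form:

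1. Physical inability to complete the flight is a scored outcome of the stair test. It is not a category 2 study withdrawal, and the participant stays in the walking analyses.
2. Score ascent and descent separately, with inability ranked worst: for example 7/time in stairs per second, and 0 if unable in that condition. If only one trial is completed, use that trial.
3. Code tests not done for other reasons (equipment fault, refusal, lack of time) as missing, not as 0.
4. Compare conditions with a Wilcoxon signed-rank test, and state that people unable in both conditions have a zero difference and do not inform it.
5. Report able/unable counts by condition, including the number of discordant pairs in each direction, and list times in completers alongside.

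No procedure or eligibility criterion changes. The downsides are small: speed is less familiar than seconds, which the listed times offset, and a rank test is slightly less efficient if everyone completes. Speed with a rank test is one workable choice. The essential parts are a prespecified score for inability and the counts by condition.

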Protocol Title

Post stroke walking kinematics using the Honda Walking Assist (HWA) robotic exoskeleton

Principle Investigator: [name] PhD, PT, NCS

Department of Physical Therapy

College of St. Scholastica [name] [contact] [contact] [contact]

Co-Investigators: [name] PhD, PT

Department of Physical Therapy

College of St. Scholastica [name] [contact] [contact] [contact]

[name] PT, DPT

Department of Physical Therapy

College of St. Scholastica [name] [contact] [contact]

[contact]

Study Device: Honda Walking Assist designed and developed by Honda R & D

Americas, Inc.

[figure not shown]
Funding Source: Honda R & D Americas, Inc.

Initial Version: 10-2-2018

10-8-2018 Revised by AB

Study Summary:

Title	Post stroke walking kinematics using the Honda Walking	
	Assist (HWA) robotic exoskeleton	
Short Title	Post stroke walking kinematics using the HWA robotic	
	exoskeleton	
Protocol Number	TBD	
Methodology	Within-subjects design	
Study Duration	10 months	
Study Center(s)	College of St. Scholastica, maurices Community Clinic	
Main Objective	Determine the effectiveness of the HWA to alter joint	
	kinematic and EMG magnitudes in individuals post-stroke	
Number of subjects	12	
Diagnosis and main criteria	Cerebrovascular accident (CVA), ≥12 weeks but <1 year post,	
	Age: 18-85 years, Walk 10 meters with stand by assistance	
	with or without orthosis or cane	
Study Product (s)	Honda Walking Assist (HWA) robotic exoskeleton	
Duration of administration	2 Testing sessions (~5-6 hours total across the 2 sessions)	
Reference condition	Walking without HWA	
Statistical Methodology	Paired t-tests, Multiple ANOVAs	

Background and rationale:

Background of the question and study rationale:

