Here we propose to quantify the effect of the HWA on walking at the knee, ankle, trunk and arm segments during phases of the gait cycle (GC) as described by Perry. (Perry & Davids, 1992) Additionally, we will quantify the aftereffect of HWA use in these joints and segments. Quantification will include measurement of walking kinematics (joint angles), muscle activity (EMG output), ground reaction forces and Spatiotemporal gait characteristics measured in three conditions: 1) Walking at self-selected pace (control), 2) walking with the HWA (4Nm assist), 3) and immediately following HWA walking (aftereffect). Our overall hypothesis is that walking with the HWA in the (hip flexion and extension) assist mode results in reallocation of cortical motor resources to the knee, ankle, trunk and arm. We also propose that normalizing walking through optimization (activation of latent residual capacity) of previously non-optimized corticospinal motor units with the HWA will produce a short-term (or within-session) aftereffect. We hypothesize that aftereffect will be greater in individuals with less lower extremity use since their stroke. Therefore we will characterize lower extremity use by quantifying the average number of steps each participant takes using an activity monitor.

Background of the device:

The Honda Walking Assist (HWA) System (pictured below) is a robotic device developed by Honda R&D Corporation ®, Japan (https://world.honda.com/Walking-Assist/). It is controlled through software run on a tablet. The device weights 2.7 kgs and has two brushless motors that run on a lithium ion battery with an approximate running time of 60 minutes. It comes in 2 sizes with adjustable frames making it possible to fit a variety of body types/sizes.

It takes approximately 5 minutes to fit the HWA on to the user. It's computer-activated motors use hip angle information to guide assistance delivered through the thigh straps to the legs in time with the walking cycle. The maximum torque delivered is 4 Nm. Wearers have described this level of assistance as "mild" to "moderate". The goal of device use is to promote walking ease by increasing stride length and improving the step symmetry.

Honda began leasing the HWA in Japan in 2015, in January of 2018 they obtained medical device approval in the European Union. Food and Drug administration approval of the HWA in the United States is in process at this time.

Study Objectives:

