	days of use during their daily routine) Total time	~28 min	
Data Set #1	Instruct participant on use of the StepWatch (send it with them for 3	10	
	Biometrics (height, weight, leg length)	5	
	Montreal Cognitive Assessment (MoCA)	8	
	side affected, assistive devices, Orthoses, handedness)	5	
1	Demographic interview (DOB, sex, date of stroke, type of stroke, body	_	

Kinematic and EMG data collection during walking

Estimated walking distance = 296 meters
Estimated walking time = 12 minutes (calculated based on .4 m/s)
Estimated duration = 30 minutes (including rests, don and doff HWA)

Description of Measures used to characterize participants

- 1. Montreal Cognitive Assessment (MoCA)-a 16-item rapid screen of cognitive abilities designed to detect mild cognitive dysfunction (Nasreddine et al., 2005), 30 points possible.
- Activities-Specific Balance Confidence Scale (ABC)-a 16-item questionnaire with an ordinal scale designed to measure an individual's confidence in their ability to perform daily activities without falling. It has good to excellent reliability and adequate construct validity. (Botner, Miller, & Eng, 2005)
- 3. Fugl-Meyer Assessment of Motor Recovery after Stroke (FMA) The domain for lower extremity motor function will be used (Sections E and F). It has been found to be valid and reliable among individuals with stroke. (Fugl-Meyer, J‰%skˆ, Leyman, Olsson, & Steglind, 1975) 34 points possible.
- 4. Modified Tardieu Scale- A measure of resistance to passive movement at different movement velocities used to quantify the dynamic component of the muscle spasticity. It has been found to be a valid and reliable method of quantifying these features of spasticity in adults with stroke. (Singh, Joshua, Ganeshan, & Suresh, 2011)
- 5. Somatosensation-Three methods of quantifying paretic lower limb somatosensation will be used. Great toe Sharp/dull (# correct/10 trials) assesses the integrity of the anterior Spinothalamic tract. (Kandel, Schwartz, Jessell, Siegelbaum, & Hudspeth, 2000) Great toe up/down testing (# correct/10 trials) assesses the integrity of the dorsal column medial lemniscal system and the higher-level task of discriminating the direction of movement (kinesthesia) (Goble, 2016), Vibration Detection Threshold is a quantitative psychophysical

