This study has a within-subjects design in which walking parameters including kinematics and muscle activity will be collected from participants during two testing sessions. For practical reasons a non-probability sample will be used. Pseudo randomization of participants into two groups will be used to control, in part, for the effect of order of testing on study outcomes.

Sample Size

The sample size for this study was calculated based on the assumption of detecting a meaningful difference in peak knee flexion angle (primary hypothesis) between the control and HWA walking conditions. To detect a mean difference of 5 degrees with a standard deviation of 5 degrees using a two-sided test and significance level of 5%, power of 80%, would require 10 participants. To allow for a 20% dropout rate 12 participants will be recruited. At the mid point of participant testing (6 participants) sample size will be recalculated and the sample adjusted if necessary to achieve appropriate power for the primary aims.

Data analysis plan

The measures collected for each subject in each condition will be compared within and across participants using paired t-tests and ANOVA. The alpha level will be set at p<0.05 to indicate statistical significance.

Data Management

Participant data collected in this study will be kept completely confidential and in compliance with HIPPA requirements. Participants will be assigned a study ID, all data collection forms and tools will use study ID therefore data will be de-identified. Data will be stored in locked cabinets, electronic data will be kept on secure, password protected computers. Data will be retained securely for three years after study publication.

References

- Botner, E. M., Miller, W. C., & Eng, J. J. (2005). Measurement properties of the Activities-specific Balance Confidence Scale among individuals with stroke. *Disability and rehabilitation*, 27(4), 156-163.
- Flansbjer, U.-B., Holmbäck, A. M., Downham, D., Patten, C., & Lexell, J. (2005). Reliability of gait performance tests in men and women with hemiparesis after stroke. *Journal of Rehabilitation Medicine*, *37*(2), 75-82.

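### Aim IV compares vertical ground reaction force with and without a 2.7 kg device, and the plan states no scaling for, or removal of, the device weight

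*Combined protocol and SAP*

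**What the plan says.** The Study Summary gives the reference condition as "Walking without HWA". The background section lists the three measured conditions: "1) Walking at self-selected pace (control), 2) walking with the HWA (4Nm assist), 3) and immediately following HWA walking (aftereffect"). The device description states "The device weights 2.7 kgs and has two brushless motors".

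Specific Aim IV is to "Determine the effect of the HWA on the magnitude of ground reaction forces (vertical load, horizontal shear, vector patterns, and center of pressure"), with each leg assessed. It states no hypothesis, direction or unit, and does not say whether a peak, a mean or an impulse is meant.

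The description of measures says "2 AMTI Force platforms will be used to quantify ground reaction forces" and adds the quantities and the sample rate, but no processing step. Weight is recorded under "Biometrics (height, weight, leg length") in Data Set 1, with no stated use in the force analysis. Data Set 2 has a further biometrics entry in the stair set-up, so weight may be taken more than once.

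The data analysis plan reads "The measures collected for each subject in each condition will be compared within and across participants using paired t-tests and ANOVA", and "The alpha level will be set at p<0.05 to indicate statistical significance". No section subtracts the device weight, scales force to body weight or to the weight carried, or adds a condition in which the device is worn without assistance.

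**The concern.** A force plate records the weight of whatever the person carries. The device is worn in one of the two conditions being compared, so part of any difference in vertical load is the device itself. A paired test is sensitive to a shift of this kind because it has the same sign and nearly the same size in each person.

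The usual scaling to body weight does not help. If both conditions are divided by the same unloaded weight, the whole shift stays in the HWA condition.

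A rise in load could then be reported as the device changing how people load their limbs. The device comes off before the aftereffect walk, so the artefact would also disappear there and look like an assist effect present only during use. Aim IV states no expected direction, so nothing in the plan would mark such a rise as suspect.

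**Working it through.** **The plan's own figure.** The sample size section concerns knee flexion, not force: mean difference 5 degrees, SD 5 degrees, two-sided 5%, 80% power, 10 participants. With d = 5/5 = 1, the noncentral t gives power 0.803 at n = 10 and 0.748 at n = 9, so 10 reproduces. I use n = 10 and the same two-sided 5% test below.

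**Inputs.** From the documents: device mass 2.7 kg, n = 10, alpha 0.05. Assumed, because the documents do not give them: g = 9.81 m/s²; body mass 60, 80 or 100 kg; SD of the within-person force difference 3%, 6% or 10% of body weight; and the share of the shift that reaches the tested variable, all or half.

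**Step 1, the shift.** Over whole strides, mean vertical force summed over both limbs equals the weight supported. Wearing the device adds 2.7 × 9.81 = 26.5 N, provided nothing else takes load. As a share of body weight:
- 2.7/60 = 4.5%
- 2.7/80 = 3.4% (3.375%)
- 2.7/100 = 2.7%

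**Step 2, what scaling does**, for this two-limb mean at 80 kg with gait unchanged:
- Raw newtons: difference 26.5 N.
- Both conditions divided by unloaded body weight: 82.7/80 − 80/80 = 3.4%.
- Each condition divided by the weight carried in it: 82.7/82.7 − 80/80 = 0.

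**Step 3, which variables carry it.** The identity is exact only for the two-limb, stride-averaged force. If the limbs share load equally, one limb's stride mean carries half the shift. In single support one limb bears the whole system, so a single-limb peak can carry nearly all of it. Peaks and single-limb means also move with walking speed, symmetry and any support from a cane or staff. Shear depends on total mass less directly. Centre of pressure and vector patterns are not simply offset.

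**Step 4, chance of a significant result with no gait change.** Let d = shift/SD and the noncentrality parameter = d × √10, with a two-sided 5% critical value of 2.262 on 9 degrees of freedom. For example, at 80 kg with the full shift and SD 3%: d = 3.375/3 = 1.125, noncentrality 3.56, probability 0.88. With half the shift: d = 1.6875/3 = 0.5625, noncentrality 1.78, probability 0.36.

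| 80 kg, n = 10 | SD 3% | SD 6% | SD 10% |
|---|---|---|---|
| Full shift (3.375%) | 88% | 36% | 16% |
| Half shift (1.6875%) | 36% | 13% | 8% |

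With the full shift, the figures for SD 3%, 6% and 10% are 99%, 56% and 25% at 60 kg, and 72%, 25% and 12% at 100 kg. All are to be read against 5%.

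**The case against.** **The plan is silent, which is not the same as wrong.** The investigators may correct for the device in processing. That stands as a limit: the finding is that no correction is stated. Silence is still not harmless here, because neither of the two ordinary defaults, raw newtons or division by unloaded body weight, removes the shift.

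**The physical identity belongs to a variable the plan does not name.** This also stands. A reader might infer that any rise in load would be only the mass worn, or that every participant's result is pushed upward by the same amount. The documents do not support either. Aim IV names no force variable, and peaks mix added mass with real change. The inclusion criteria allow an assistive device and standby assistance, and the risk section has staff keep contact during walking. Such support can bypass the plates and may differ between conditions.

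**The 88% is not the expected error rate.** A reader might take it as one. It is a single assumed case that combines the full two-limb shift with an SD of 3%. Without outside support, the two-limb stride mean should vary little within a person, so SDs of 3% to 10% suit single-limb variables better, and for those the shift is not fixed. Only the range can be defended.

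**The added load is part of the device's total effect.** The limbs do bear it, and a comparison with walking without the device can legitimately include it. That is a fair question to answer, but it differs from whether gait loading changed. Reporting both, labelled, serves both.

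**Aim IV is not the basis of the sample size.** Correct. It limits how serious the point is, not whether it holds.

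**Conclusion.** The point holds in limited form. As written, the control-versus-HWA contrast in vertical load is confounded by worn mass. The shift is 26.5 N in stride-averaged two-limb force, or 2.7% to 4.5% of body weight over assumed masses of 100 down to 60 kg, if there is no outside support. For single-limb variables, part or nearly all of this is present and cannot be separated from changes in speed, symmetry or support.

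The false-positive rate cannot be stated as one number because the documents give no force SD. At 80 kg and n = 10 it lies between about 8% and 88% across the assumed cases, and every one of those cases exceeds the nominal 5%.

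The control-versus-aftereffect contrast should be free of the shift, since the walking session allows time to take the device off. The walking schematic is not shown, so that rests on the session timing note. The knee-flexion comparison behind the sample size is not touched by this force artefact. The change should be made, but it does not threaten the main result.

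**What to change.** In Specific Aim IV and the data analysis plan:

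1. Divide vertical force, and shear, by the weight carried in that condition: body weight for control and aftereffect walking, body plus device weight for HWA walking. Use 2.7 kg or the weighed mass of the size worn.
2. Name the force variable tested (peak, mean or impulse) and whether it is per limb or summed.
3. Base any conclusion that gait loading changed on the scaled values.
4. Also report unscaled values, labelled as including the device weight, for readers who want the total effect of wearing it.

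Scaling brings the offset in mean total vertical load to zero. It does not correct for load taken by a cane or by staff, so that remains a caveat when the results are interpreted.

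The cost is about one extra line of analysis. Device weight is known and body weight is already collected, so no new visit or measurement is needed.
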